6.2 Secondary efficacy endpoints

Secondary efficacy endpoints will be analysed on the m-ITT set and on PP set.

6.2.1 Change from baseline in IOP

Descriptive statistics will be performed on IOP at 08:00, 10:00 and 16:00 for the contralateral eye at each assessment time (i.e., baseline, Week 6 and Week 12). Change from baseline to Week 6 and change from baseline to Week 12 will be described as well. These descriptions will also be performed by country and by possible impact of COVID-19 pandemic classes.

Using the same MMRM as for the main analysis of the primary efficacy endpoint, 95% CI of the adjusted mean difference between treatment groups will be estimated for:

- Change from baseline in IOP at Week 12 at 08:00, 10:00 and 16:00 in the contralateral eye
- Change from baseline in IOP at Week 6 at 08:00, 10:00 and 16:00 in the worse eye and in the contralateral eye

As for the primary endpoint, sensitivity analyses based on ANCOVA: using i) the LOCF method and ii) observed value at Week 12 will be performed for the contralateral eye. The 95% CI of the adjusted mean difference between treatment groups in the change from baseline to Week 12 in IOP will be provided.

ANCOVA on the change from baseline in IOP at Week 6 will also be performed for the worse eye and for the contralateral eye. The 95% CI of the adjusted mean difference between treatment groups will be provided.

The exploratory analysis on the impact of circadian rhythm will also be assessed at Week 6 by using the same model described in Section 6.1.4 for this parameter.

6.2.2 Other analyses on IOP

Frequency distribution of patients with IOP <18 mmHg and IOP \geq 18 mmHg will be described by treatment group at each assessment time (Baseline [Day 1] at 08:00, 10:00 and 16:00, Week 6 at 08:00, 10:00 and 16:00 and Week 12 at 08:00, 10:00 and 16:00), separately for the worse eye and the contralateral eye.

Descriptive statistics will be performed on IOP at 08:00, 10:00 and 16:00 and on changes from baseline for the worse eye and for the contralateral eye at each assessment time (*i.e.*, baseline, Week 6 and Week 12), depending on the History of glaucoma or ocular hypertension.

Descriptive statistics will be performed on the mean diurnal IOP at baseline, Week 6 and Week 12. Change from baseline to Week 6 and change from baseline to Week 12 will be described.

6.2.3 Global assessment of efficacy by the investigator

Global judgment of efficacy by investigator will be assessed on a 4-point ordinal scale (Very satisfactory, Satisfactory, Not very satisfactory, Unsatisfactory).

Assessment of Azopt® efficacy will be presented by frequency distribution for each modality and frequency distribution after regrouping 'very satisfactory' with 'satisfactory', and 'not very satisfactory' with 'unsatisfactory'.

Assessment of LT4032 or Lumigan® efficacy will be presented by frequency distribution for each modality and frequency distribution after regrouping 'very satisfactory' with 'satisfactory', and 'not very satisfactory' with 'unsatisfactory', at Week 6 and Week 12. After regrouping in 2 classes, comparison of treatment groups at Week 6 and Week 12 will be performed using a CMH test stratified by country.

7 SAFETY ANALYSIS

Safety endpoints will be analysed on the Safety set, by treatment group except when specify on the Azopt® Safety set overall.

7.1 Conjunctival hyperaemia – Slit lamp examination

Conjunctival hyperaemia assessed for each eye using the McMonnies photographic 6-point ordinal scale from 0 to 5 will be presented by frequency distribution at each assessment time (screening, baseline [Day 1], Week 6 and Week 12), for the worse eye and contralateral eye. Comparison between treatment groups will be performed at Week 6 and at Week 12, using a CMH test with modified ridit scores stratified by country, separately for the worse eye and for the contralateral eye.

In addition, frequency distribution of change from baseline will be presented for conjunctival hyperaemia at Week 6 and Week 12 for the worse eye and contralateral eye. The following categories will be defined and presented: i) improvement (*i.e.*, decrease of symptom score from baseline), absence stable, presence stable, worsening (*i.e.*, increase of symptom score from baseline), ii) improvement, no change, worsening, iii) improvement of more than 1 point (*i.e.*, change from baseline <-1 , no significant change (*i.e.*, change from baseline ≥-1 and ≤ 1), worsening of more than 1 point (*i.e.*, change from baseline >1). Comparison of changes from baseline in 3 classes (improvement, no change, worsening) for conjunctival hyperaemia between treatment groups will be performed at Week 6 and Week 12, using a CMH test with modified ridit scores stratified by country, separately for the worse eye and for the contralateral eye.

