1.5 Sample size considerations

The sample size determination was based on the primary efficacy endpoint, *i.e.*, the change in IOP at the three time points (08:00, 10:00, 16:00) after 12 weeks of treatment, in the worse eye.

Non-inferiority of T4032 *versus* Lumigan® 0.01% will be tested with a non-inferiority margin of 1.5 mmHg. Non-inferiority will be concluded if it is achieved for each of the three time points 08:00, 10:00 and 16:00.

The evaluation will be based upon a two-sided 95% confidence interval (CI) on the difference in mean change in IOP after 12 weeks of treatment.

With data available for 180 patients in each arm, there is more than 90% power to show that the T4032 unpreserved eye drops is non-inferior to Lumigan® 0.01% preserved eye drops. The hypothesis was based on the 1.5 mmHg margin, assuming no difference between the two groups (average difference of 0 mmHg), and a standard deviation of 3 mmHg and correlation between time-points of 0.7 on the primary efficacy variable.

Evaluable patients are defined as randomised patients having received at least one dose of IMP (T4032 or Lumigan®) and with at least one post-randomisation efficacy assessment.

Accounting for a 10% dropout/non-evaluable rate, 400 initially treated patients were expected to be randomised.

The sample size of 400 randomised patients is also justified to collect enough safety data. Number of screened patients depends on the screen failure rate and was estimated at 668 patients.

At the end of the recruitment period, 723 patients were screened and 485 patients were randomised.

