4.2 Premature discontinuation and missing data

A patient who prematurely discontinues from the study should have, if possible, a premature discontinuation visit with the assessment planned on the final visit. This visit should take place as soon as possible after the patient stops taking the IMP.

For patients who prematurely discontinue from the study during the COVID-19 outbreak, the premature discontinuation visit was requested by visit on site if possible, else by phone.

For these patients who prematurely discontinue from the study, evaluations performed during the premature withdrawal visit will be considered as the first unobserved scheduled visit whatever their actual dates. If the premature withdrawal visit occurs after the discontinuation of the treatment, evaluations will be reviewed during the blind review meeting prior to the database lock to confirm their use thereof.

Otherwise, missing data will not be replaced, except for sensitivity analysis of the primary endpoint (see Section 6.1.2). Based on the Last Observation Carried Forward (LOCF) method, missing values at Week 12 will be replaced by the post-randomisation last available value. For the primary efficacy endpoint, a sensitivity analysis considering the post-randomisation last available value will be performed for the contralateral eye (see Section 6.2.1).

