7.5 Corneal staining according to Oxford grading scheme

The Oxford 0-5 grading scheme assesses the staining of the corneal area.

The CFS score (ranging from 0 to 5) will be calculated and frequency distribution will be presented at screening, baseline (Day 1), Week 6 and Week 12, for the worse eye and for the contralateral eye. Comparison of the CFS score between treatment groups will be performed at Week 6 and at Week 12 using a CMH test with modified ridit scores stratified by country, separately for the worse eye and for the contralateral eye.

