7.6 Far best corrected visual acuity

Far best corrected visual acuity in LogMar will be summarised at screening, baseline (Day 1) and Week 12 using usual descriptive statistics for continuous variable, for the worse eye and for the contralateral eye.

Frequency distribution in classes (*i.e.*, values from 1/10 to 10/10, including NA category, with non-integer numbers rounded to the nearest integer) will also be presented.

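### For patients who leave before Week 6, the exit visual acuity falls in no summary table, and the exit grades are in the Week 6 but not the Week 12 CMH tolerability tests

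*SAP*

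**What the plan says.** Two rules in SAP 4.2 decide where exit data go. First, "evaluations performed during the premature withdrawal visit will be considered as the first unobserved scheduled visit whatever their actual dates". Second, "Otherwise, missing data will not be replaced, except for sensitivity analysis of the primary endpoint". The same section asks for the final-visit assessments at the exit visit where possible, so an exit acuity is meant to be collected.

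The safety sections are then written by visit. For hyperaemia, SAP 7.1 states: "Comparison between treatment groups will be performed at Week 6 and at Week 12, using a CMH test with modified ridit scores". For corneal staining, SAP 7.5 states: "Comparison of the CFS score between treatment groups will be performed at Week 6 and at Week 12". Sections 7.2, 7.3, 7.4, 7.8 and 7.9 do the same for each symptom, each ocular sign and the two tolerance ratings. Only the two symptom total scores (7.2, 7.3) are compared by an MMRM over both visits.

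For visual acuity there is no Week 6 summary. SAP 7.6 says it "will be summarised at screening, baseline (Day 1) and Week 12", and the footnote to the Table 5.15 shell names the same three times. Section 7.7 lists visual field and funduscopy at Week 12 together with the screening results.

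**The concern.** Safety is a stated secondary objective, comparing an unpreserved with a preserved drop. Patients who stop early because the drop is poorly tolerated are among the most informative for that comparison. Adverse events are one of the two grounds on which the protocol synopsis has the investigator discontinue a patient, so early exit can depend on the outcome being graded.

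Two things could be lost. The exit acuity of an early leaver has no row in any table. If one arm loses more patients early to redness or staining, its Week 12 distribution looks better because those patients are no longer in it. For IOP, the SAP recognises that dropout could affect the treatment comparison and plans an MMRM with LOCF and observed-case sensitivity analyses (6.1.1, 6.1.2). The ordinal tolerability scales have no counterpart.

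**Working it through.** **The plan's own figures.** The SAP gives no figure for the safety comparisons. Its sample-size statement (1.5) concerns IOP: non-inferiority is "tested with a non-inferiority margin of 1.5 mmHg", with "a standard deviation of 3 mmHg and correlation between time-points of 0.7 on the primary efficacy variable". With 180 per arm, SE = 3 × √(2/180) = 0.316 and 1.5/0.316 − 1.96 = 2.78. Power is 99.7% at one time point and 99.3% for all three, consistent with the stated more than 90%; 360/0.9 = 400 also matches. None of this changes here. The one figure carried forward is the 485 patients randomised 1:1, about 242 per arm.

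**Where the exit visit goes (SAP 4.2 applied to each analysis).**

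| Analysis | Leaves before Week 6 | Leaves between Week 6 and Week 12 |
|---|---|---|
| Exit visit analysed as | Week 6 | Week 12 |
| Week 6 CMH tests | included, exit grade | included, Week 6 grade |
| Week 12 CMH tests | absent | included, exit grade |
| Symptom total scores, MMRM | included through Week 6 | included |
| Acuity, Tables 5.15 and 5.16 | no row | Week 12 row |
| AEs leading to withdrawal (7.10) | included | included |

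The acuity gap follows from 4.2 and 7.6 alone and needs no assumption about dropout.

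**Does the MMRM use a patient seen only at Week 6?** Assumed: Week 6 to Week 12 correlation 0.6, and 10 of 100 patients in one arm with Week 6 data only. Raising those ten Week 6 scores by 3 SD moves the Week 12 treatment contrast by −0.6 × 3 × 10/100 = −0.18 SD. Such patients do inform the Week 12 estimate.

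**Size of the shift in a Week 12 contrast (illustration).** Assumed: 20% worsened among patients observed at Week 12 in both arms, and every early leaver counted as worsened. With early-exit proportion d, the rate including leavers is 0.20(1 − d) + d = 0.20 + 0.80d. The arm difference is 0.80 × (d for T4032 − d for Lumigan), against an observed Week 12 difference of 0.

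| Early exit, T4032 / Lumigan | Patients out of 242 | Difference including leavers |
|---|---|---|
| 1% / 1% or 5% / 5% | 2.4 / 2.4 or 12.1 / 12.1 | 0.0 points |
| 1% / 3% | 2.4 / 7.3 | −1.6 points |
| 2% / 5% | 4.8 / 12.1 | −2.4 points |
| 3% / 7% | 7.3 / 16.9 | −3.2 points |
| 5% / 10% | 12.1 / 24.2 | −4.0 points |

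**Power (simulation, all inputs assumed).** 240 per arm, a six-grade scale, correlation 0.7, a true shift of 0.25 SD against one arm, the reddest patients leaving before Week 6, and an unstratified Mann-Whitney test at 5% in place of the country-stratified CMH. Sets A and B differ in the assumed grade cut-points.

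| Early exit, worse / better arm | A: Week 6 test | A: Week 12 test | A: worst grade | B: Week 12 test | B: worst grade |
|---|---|---|---|---|---|
| 1% / 1% | 0.72 | 0.74 | 0.76 | 0.58 | 0.62 |
| 5% / 1% | 0.72–0.73 | 0.51 | 0.76–0.78 | 0.35 | 0.63 |
| 8% / 2% | 0.72 | 0.43 | 0.76 | 0.29 | 0.60 |

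Absolute power depends on the cut-points, but the pattern does not. The Week 12 test loses power as exit becomes unequal, while the worst-grade test, and in set A the planned Week 6 test, do not. If redness only raises the chance of leaving, instead of fixing who leaves, Week 12 power at 5%/1% was 0.61 rather than 0.51.

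**The case against.** A reader might infer that the Week 12 tests contain only patients who tolerated the drop, or that early leavers are in no Week 12 comparison at all. The documents support neither. Under 4.2 a patient who leaves after Week 6 has the exit visit analysed at Week 12, and the MMRM of the symptom total scores keeps patients who have only a Week 6 value.

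Nor would an intolerance signal be hidden. The Week 6 tests contain the exit grade. AEs leading to IMP withdrawal are tabulated by arm (7.10.1, 7.10.2), as are reasons for discontinuation (5.1, Table 1.25). Those reasons also include patient's request, loss to follow-up and the COVID-19 crisis, so early exit is not only an intolerance outcome. These points stand and limit the concern.

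On acuity, it can be argued that the schedule heads the Week 12 column as the final or premature discontinuation visit, and that a variable not summarised at Week 6 has Week 12 as its first unobserved visit. But 4.2 assigns the evaluations of the exit visit together, and Listing 1.2 has one analysis visit for each visit, which points to Week 6. At best the text is ambiguous. Individual values do appear in the by-patient listings (SAP section 3), so they are left out of the tables rather than lost.

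A worst-grade test has its own bias: completers have two chances of a high grade and early leavers one. That objection is correct, and it keeps such a test optional.

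**Conclusion.** The point holds in a limited form. For patients who leave before Week 6, the exit acuity has no summary row, visual field and funduscopy are specified only at Week 12, and the Week 12 CMH tests of hyperaemia, individual symptoms, ocular signs, corneal staining and tolerance omit them. The acuity part rests only on reading 4.2 as assigning the whole exit visit to one analysis visit.

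The effect on the Week 12 tests is conditional. It is zero in the illustration when early exit is equal by arm, and 1.6 to 4.0 percentage points across the unequal rates tried. Those rates, and the power figures, are assumptions: the SAP plans for 10% dropout or non-evaluable patients overall and gives no early-exit rate by arm. A reader might conclude that the plan cannot detect a tolerability difference under unequal exit. That does not follow, because the planned Week 6 test kept power of about 0.72 in the same scenario.

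Exit examinations after the last dose are used only if the blind review confirms them, and exits handled by phone give no eye examination, so some leavers may contribute to neither visit. The primary IOP conclusion is not affected.

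**What to change.** 1. In SAP 7.6 and Tables 5.15 and 5.16, keep the Week 12 row and add a row for the last post-baseline value (Week 12 or premature discontinuation visit). Adding the row avoids mixing time points in the Week 12 summary.
2. In 7.7, state that the visual field and funduscopy listing includes results from the premature discontinuation visit.
3. Optionally, add one supportive CMH analysis per ordinal tolerability scale on the last or worst post-baseline grade, including the exit visit. Label it descriptive, note that early leavers contribute one grade and completers two, and leave the by-visit tests unchanged.

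Items 1 and 2 cost a sentence each and one table row per eye, from data already collected. Item 3 costs more: for hyperaemia (2 eyes), symptoms (6 × 2 settings), signs (5 × 2 eyes) and staining (2 eyes) it adds 2 + 12 + 10 + 2 = 26 unadjusted comparisons, before any for the tolerance ratings.

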Secondary Efficacy Endpoints	
 Change from baseline to Week 12 in IOP at the three time points (8:00, 10:00 and 16:00) in the contralateral eye. 
Others efficacy endpoints will be analysed:
 
 Change from baseline to Week 6 in IOP at the three time points (8:00; 10:00; 16:00) in the worse eye and in the contralateral eye. Efficacy assessed by the investigator.
Safety Endpoints	
 Conjunctival hyperaemia on McMonnies scale at Week 6 and Week 12. Change from baseline of the conjunctival hyperaemia on McMonnies scale in 3 classes (improvement, no change, worsening) at Week 6 and Week 12. Score of each ocular symptom throughout the day and the sum of these scores. Score of each ocular symptom upon instillation and the sum of these scores. Score of each ocular sign. Corneal fluorescein staining (Oxford grading scheme). Far Best Corrected Visual Acuity expressed in Log MAR. Ocular tolerance assessed by the investigator.

	
 • Ocular tolerance assessed by the patient. • Ocular and systemic AE by System Organ Class and Preferred Term.

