- Residuals will be plotted against predicted values to check the assumption of heteroscedasticity
- Plots of residuals and studentised residuals will be performed to detect outliers. Cook's distance will also be computed. If any outliers are detected, then main model will be performed with and then without them
- For ANCOVA models, Levene's test will also be performed to check the homogeneity of variances

For each model (MMRM or ANCOVA), if there is a strong violation of normality assumption (or violation of homogeneity of variances for ANCOVA), in addition to the initial model, a rank transformation will be done, and the model will be applied to ranks.

The acceptable risk of error for the statistical tests will be set at 5%, except for treatment by covariates interactions. For those interactions, the level of significance will be set at 7%.

For ordered qualitative variables, treatment groups will be compared using Cochran-Mantel-Haenszel (CMH) test stratified by country, with modified ridit scores and “row mean score differ” option.

Tables and Listings will be provided in separated documents except the listing of Deaths, Other Serious adverse events, discontinuations due to adverse events and other adverse events of special interest (see Section 7.10.3).

All individual data will be described in the listings 16.2, by treatment and by patient as follows: discontinued patients, protocol deviations, patients excluded from the efficacy analysis, demographic data, compliance, individual efficacy response data, adverse event listings, listing of individual laboratory measurements.

All individual data of eCRF will be described in the listing 16.4, by patient.

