4.3.11 Change from baseline in classes

Change from baseline in classes will be defined as detailed below:

In four classes:

- Improvement (Decrease of score from baseline): Change from baseline <0
- Absence stable: Change from baseline = 0 and absence of symptoms
- Presence stable: Change from baseline = 0 and presence of symptoms
- Worsening (Increase of score from baseline): Change from baseline >0

In three classes compared to 0:

- Improvement (Decrease of score from baseline): Change from baseline <0
- No change: Change from baseline = 0
- Worsening (Increase of score from baseline): Change from baseline >0

In three classes compared to -1/1:

- Improvement of more than 1 point: Change from baseline <-1
- No significant change: Change from baseline \geq -1 and \leq 1
- Worsening of more than 1 point: Change from baseline >1

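### No planned test of conjunctival hyperaemia uses both the full 0-5 grade and the Day 1 grade, so some precision is given up; one baseline-adjusted test per eye and visit would recover it at almost no cost

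*SAP*

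**What the plan says.** SAP 7.1 describes the measurement as "Conjunctival hyperaemia assessed for each eye using the McMonnies photographic 6-point ordinal scale from 0 to 5". It then plans two between-arm tests, each done separately for the worse and the contralateral eye.

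- **Grade at the visit.** "Comparison between treatment groups will be performed at Week 6 and at Week 12, using a CMH test with modified ridit scores stratified by country". Day 1 does not enter. The p-value goes in Tables 5.1 and 5.3.
- **Change from Day 1.** "Comparison of changes from baseline in 3 classes (improvement, no change, worsening) for conjunctival hyperaemia between treatment groups will be performed", again by country-stratified CMH. SAP 4.3.11 defines the top class as "Worsening (Increase of score from baseline): Change from baseline >0", whatever the size of the rise. The p-value goes in Tables 5.2 and 5.4.

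Table 5.2 also shows the count at every integer change, a four-class split and a more-than-one-point split. None of these has a p-value.

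Both choices have a source. The protocol synopsis lists the grade as a safety endpoint and then "Change from baseline of the conjunctival hyperaemia on McMonnies scale in 3 classes (improvement, no change, worsening) at Week 6 and Week 12". The method is the SAP's general rule in section 3: "For ordered qualitative variables, treatment groups will be compared using Cochran-Mantel-Haenszel (CMH) test stratified by country, with modified ridit scores". For scores analysed by model the SAP does use baseline: section 3.5 requires it in the MMRM and ANCOVA models, and 7.2 adjusts the change in the 0-18 symptom total for its baseline value.

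**The concern.** Each planned test discards something the other keeps. The grade test carries differences between patients that were already there on Day 1. The change test refers to Day 1 but ties all rises together and all falls together. Which of the two is stronger depends on how closely a patient's grades correlate over time, and that is not known in advance.

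At stake is the precision of the hyperaemia comparison between an unpreserved and a preserved product, in a trial where evaluating safety is a stated secondary objective. The Day 1 grade is already collected, so the lost precision costs nothing to recover. The IOP non-inferiority result does not depend on it.

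**Working it through.** **The plan's own figure.** There is none for hyperaemia. The only power statement concerns IOP (SAP 1.5), and it holds. With 180 per arm, 1.5/(3 x sqrt(2/180)) - 1.96 = 4.74 - 1.96 = 2.78, which is 99.7% power per time point. With correlation 0.7 it is 99.3% for all three jointly. Also 360/0.9 = 400. This says nothing about hyperaemia.

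**Inputs.** From the SAP: 1:1 allocation, 485 randomised, 10% loss, 5% two-sided tests. This gives 485 x 0.9 / 2 = 218 per arm. Country strata: the Table 1.4 shell lists 17 countries, and pooling the three listed ones named in 4.3.1 gives 17 - 3 + 1 = 15; runs with 14 and with 15 strata agree closely. Assumed, because the documents give nothing: latent grade SD 0.7-1.1, Day 1 to visit correlation rho 0.3-0.7, and the size and form of the arm difference.

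**Why adjustment helps.** On a continuous scale with equal variance at both visits, the variance of the arm comparison is proportional to 1 for the visit grade, 2(1 - rho) for the change, and 1 - rho^2 for the grade adjusted for Day 1.

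| rho | grade | change | adjusted |
|---|---|---|---|
| 0.3 | 1 | 1.40 | 0.91 |
| 0.5 | 1 | 1.00 | 0.75 |
| 0.7 | 1 | 0.60 | 0.51 |

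Grade and change swap places at rho = 0.5. Adjustment is smallest throughout, since 1 - rho^2 = (1 - rho)(1 + rho).

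**What collapsing costs.** Take assumed shares at +1/+2/+3 of 20/14/6% against 25/8/2%. Any worsening is 40% against 35%, but worsening by more than one grade is 20% against 10%. The three-class test has 18% power and the uncollapsed change 36%. This scenario compares the two change tests only.

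**Simulation 1: rank ANCOVA.** Latent normal grades rounded to the scale, 218 per arm, 14 strata, 4000 runs, SD 0.9, arm difference 3.1 x SD x sqrt(1 - rho^2) x sqrt(2/218). Power in %:

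| rho | sign of change (planned) | uncollapsed change | grade (planned) | rank ANCOVA | gain over better planned test |
|---|---|---|---|---|---|
| 0.3 | 55 | 60 | 76 | 79 | 79 - 76 = 3 |
| 0.5 | 61 | 64 | 70 | 78 | 78 - 70 = 8 |
| 0.7 | 62 | 65 | 51 | 72 | 72 - 62 = 10 |

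Over the whole grid of SD and rho, the gain over the better planned test is about 2-11 points, and over the sign test alone about 9-27. Uncollapsing the change without adjusting gains only about 3-8 over the sign test. If 10-15% of one arm worsens by 2 SD, rank ANCOVA gains about 2-16 over the better planned test.

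**Simulation 2: fixed shift of 0.25 SD.** 240 per arm, 1500 runs, with an ordinary linear ANCOVA on grade (Day 1 grade and country) as reference:

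| rho | sign | uncollapsed change | grade | ANCOVA | gain over better planned test |
|---|---|---|---|---|---|
| 0.3 | 53.2 | 59.3 | 71.1 | 76.6 | 5.5 |
| 0.5 | 61.7 | 68.5 | 71.1 | 80.5 | 9.4 |
| 0.7 | 82.9 | 86.6 | 72.3 | 91.7 | 8.8 |

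With 200 or 240 per arm and two sets of grade cut-points, the gain is 4-12 points. When 10-15% of one arm worsens by 1.5-2.5 SD, power is 18/23/42% for sign, 27/42/67% for uncollapsed change, 24/42/66% for grade and 43/77/91% for ANCOVA. That gain of 19-35 points belongs to linear ANCOVA; ranks compress large grades, so the rank version gains less.

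Null rejection was 4-6% for every test. Monte Carlo error near 70% power is about sqrt(0.7 x 0.3/1500) = 1.2 points.

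**The case against.** The strongest reply is that the plan already tests the full grade. That stands. The unadjusted grade test is unbiased under randomisation and keeps severity; in the minority scenarios it almost matches the uncollapsed change (24/42/66% against 27/42/67%). A reader might infer from the sign-only change test that the hyperaemia comparison as a whole cannot see severity, or that its power rises from 61% to 78% with the fix. The documents do not support either reading: the first overlooks the grade test, and the second measures the gain against the weaker planned test. At that setting the grade test has 70%, so the gain is 8 points.

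It also stands that most of the gain under a shift comes from adjusting for Day 1, not from undoing the three classes. The three-class change is a protocol endpoint, and SAP 7.1 gives one test to each listed hyperaemia endpoint. Ocular signs and corneal staining get no baseline-referenced test at all. Only the protocol synopsis is available here, so no weight can rest on the lack of a stated reason for the classes. The tables still display severity by arm.

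A fair technical criticism is that simulation 1 ties the arm difference to rho, so the effect shrinks as rho rises and the grade test is bound to fall at 0.7. Simulation 2 holds the shift fixed and reaches the same ordering, with adjustment ahead in every cell. What the objections leave untouched is that no planned test combines full grade and Day 1.

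**Conclusion.** The gap is real and modest. SAP 7.1 contains one test with full severity and no baseline, and one with baseline and no severity. A prespecified test that uses both was better than either in every alternative simulated, with type I error near 5%. Against the better planned test the gain is about 2-11 points of power under a uniform shift and about 2-16 points when a minority worsens markedly. Against the sign test alone it is about 9-27 points under a shift, but that is not the measure of what the plan loses.

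All of these sizes rest on assumed SD, correlation and effect, since the documents supply none. The direction follows from the variance argument. Nothing here calls for demoting the protocol's three-class comparison, and nothing touches the IOP conclusion. This is a cheap improvement, not a defect that threatens the trial.

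**What to change.** In SAP 7.1, add one test per eye at Week 6 and at Week 12 on the full 0-5 grade, adjusted for the Day 1 grade and stratified by country. Rank ANCOVA fits the existing machinery: within each country (grouped as in 4.3.1) rank the visit grade and the Day 1 grade, take residuals of the first on the second, and compare arms with the stratified mean-score CMH test.

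State in advance that this is the lead full-grade comparison. Keep the three-class comparison and the unadjusted grade test as planned. Print the new p-value in the hyperaemia tables (5.1 to 5.4, by eye) and list the addition in SAP section 8. Recruitment had ended when the SAP was written, so the change must be fixed before database lock and unblinding.

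The cost is a few sentences and a few lines of code, with no new data, visits or patients. The one drawback is multiplicity: 2 tests x 2 eyes x 2 visits = 8 p-values become 12, none adjusted. Naming the lead test beforehand limits the harm.
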